4 STUDY VISITS AND PROCEDURES

Study timeline:

Information relating to study sent via letter		
Opportunity for self-enrolment, clinic enrolment, phone enrolment		A
Consent		B
Randomisation	Intervention	Control
Baseline data collection	C D E	C D E
3 months	F G H	F G
6 months	F G	F G
12 months	D E F G H	D E F G
A	Survey screening for inclusion/exclusion criteria sent to all potential participants	
B	Children meeting inclusion criteria and interested in study referred to PICF and consent form	
C	Demographic information (as part of the baseline questionnaire)	
D	Spirometry	
E	CFQ-R & EQ-5D-Y (as part of the baseline questionnaire)	
F	Data download from EPIC (admissions, LOS, contacts with CF team)	
G	Online follow up questionnaire	
H	Semi structured interviews	

Description of intervention

Remote symptom monitoring and automated treatment plans:

Participants randomised to the intervention arm will receive onboarding material (Appendix 7) detailing instructions of how to access and use the remote monitoring system via the RCH portal.

Participants will be asked to complete two surveys:

1. Baseline symptom survey (Appendix 8)

Participants will be prompted to complete survey by a push notification sent to their mobile phone and built into EPIC at the:

- Commencement of the trial;
- Each month post commencement of the trial; and
- After each exacerbation is detected.

2. Twice weekly symptom survey (Appendix 8)

Participants will be prompted to complete a survey by a push notification sent to their mobile phone and built into EPIC twice a week

The survey is a validated tool for detecting pulmonary exacerbations in people with CF[29].

A score is assigned to each survey field. Every symptom-monitoring questionnaire completed by the patient or patient's family is compared to their last known baseline questionnaire.

If the frequency or severity of **two or more symptoms** have worsened compared to baseline, the **Exacerbation Pathway** is triggered (Appendix 9 for exacerbation calculations).

If the system detects an exacerbation, it will send an automated treatment plan out to the patient and their caregiver including:

- Directions to commence a specific antibiotic
- Directions to change/or increase airway clearance and inhalation therapy.

Information regarding antibiotic, airway clearance and inhalation therapy prescription will be extracted from the participant's EPIC file.

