At this time participants will be asked to complete their **symptom survey on a daily basis**.

A message will be sent to the CF team alerting them of the exacerbation and the results of the symptoms survey. The RCH respiratory lab will book a telehealth appointment to perform home lung function to provide further detail of the exacerbation. Lung function will be performed at the start of the exacerbation and at 10-14 days later.

10-14 days after the exacerbation pathway is triggered, the program will assess if symptoms reported in the daily symptom survey have returned to baseline or not.

If the patient symptoms return to (or are better than baseline) on day 10-14:

Study Name: Acceptability, feasibility and impacts of remote symptom monitoring and automated treatment plans in children with Cystic Fibrosis (CF) on highly effective modulators: a pilot randomised controlled trial.

Protocol Number: 91117

Version & date: version 2, 28.10.2022

1. The program re-assigns the non-exacerbation tasks:
 - a. Monthly baseline questionnaire
 - b. Symptom-monitoring questionnaire (twice a week).
2. An automated In Basket message will be sent to the CF team notifying them that the exacerbation has ceased.
3. An automated message is sent to notify the participant that symptoms have improved and the exacerbation has ceased, instructing them to cease antibiotics (if not already), return to baseline airway clearance and inhalation therapy and complete their normal twice weekly symptom surveys.

If the patient symptoms do not improve on day 10-14 (Extended Exacerbation):

1. An In Basket Message will be sent to the CF team prompting for a clinical review via telehealth.
2. A notification will be sent to the participant via the portal notifying them that their symptoms have not become better and expect contact from the treatment in 24 hours.

The RCH EMR team have designed a workflow for the pilot to help assist in ensuring all aspects of care are completed.

Participants randomised to the intervention group will also receive all aspects of usual care in

addition to the above information, including quarterly visits to the CF clinic.

Usual Care:

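### A baseline survey prompted at detection of an exacerbation can become the reference for the day 10-14 recovery check, so a child who is only partly better could be sent the automated closure message

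*Protocol*

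**What the plan says.** All the relevant text is in Protocol section 4, Description of intervention.

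- **When a baseline is collected.** The baseline symptom survey is prompted at the start of the trial, monthly, and "After each exacerbation is detected".
- **What it is used for.** "Every symptom-monitoring questionnaire completed by the patient or patient's family is compared to their last known baseline questionnaire". Worsening of two or more symptoms against that reference opens the exacerbation pathway, and the symptom survey then becomes daily.
- **The recovery check.** Ten to fourteen days after the trigger, "the program will assess if symptoms reported in the daily symptom survey have returned to baseline or not".
- **Closure branch.** "If the patient symptoms return to (or are better than baseline) on day 10-14", three things follow. First, "The program re-assigns the non-exacerbation tasks", which are the monthly baseline questionnaire and the twice-weekly survey. Second, the CF team is notified that the exacerbation is over. Third, the participant is told that "symptoms have improved and the exacerbation has ceased, instructing them to cease antibiotics (if not already"), and to go back to usual airway clearance and inhaled treatment.
- **Review branch.** "If the patient symptoms do not improve on day 10-14 (Extended Exacerbation"), then "An In Basket Message will be sent to the CF team prompting for a clinical review via telehealth", and the family is told to expect contact.

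The scoring detail is referred to Appendix 9 and the surveys to Appendix 8. Neither is in the text supplied.

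**The concern.** A test of return to baseline protects the child only if the baseline describes the child when well. Section 4 asks for a fresh baseline at a point when the child has just been found to be unwell, and makes the latest baseline the comparator. If that survey is answered at flare level, the bar for recovery drops to the level of the illness itself.

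The reference decides between two very different actions: a prompted telehealth review, or an automated message to stop antibiotics and step down therapy with the CF team told that the episode is over. The section describes no clinician step before the closure message goes out.

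There would also be an effect on the data. The EPIC reports for the intervention group include the number and length of exacerbations. Premature closure would shorten the recorded length. A baseline left at flare level would make a new trigger harder to reach until the next baseline is completed.

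**Working it through.** No sample size, power or event figure is involved, so the check is a trace of the stated rules.

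**Step 1: when the extra baseline is prompted.** Section 4 and the synopsis use forms of the verb *detect* for the moment when the system triggers the pathway. Section 4 uses *ceased* for the end. The natural reading of "After each exacerbation is detected" is therefore at or soon after the trigger, although no interval is given.

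**Step 2: which baseline is the reference.** The comparison rule ("Every symptom-monitoring questionnaire completed by the patient or patient's family is compared to their last known baseline questionnaire") covers every symptom questionnaire. The daily survey during an exacerbation is the same symptom survey given more often, so the rule covers it too. Nothing shown excludes a baseline completed while the pathway is open.

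**Step 3: apply the day 10-14 test under each reference.** The scores below are illustrative assumptions, with higher meaning worse. Before the flare, cough is 1 and sputum 1. At the trigger, cough is 3 and sputum 3, so two symptoms are worse and the pathway opens. The prompted baseline is assumed to be completed at that level (3, 3). Both symptoms move together, so the result does not depend on how many symptoms must have returned.

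| Day 10-14 state (cough, sputum) | Reference: last baseline before trigger (1, 1) | Reference: baseline completed during flare (3, 3) |
|---|---|---|
| Recovered (1, 1) | Equal: closure | Better: closure |
| Partly better (2, 2) | Both still worse, not returned: review | Both better: **closure** |
| Unchanged (3, 3) | Both still worse: review | Equal, so meets the closure test, but also fits the review heading: **conflict** |
| Worse than at detection (above 3, 3) | Review | Review |

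**Step 4: read the result.** The partly better child moves from review to closure purely because of the reference. For the unchanged child, the text gives two answers. The rows are categories chosen for the trace and carry no information about how many children would fall in each.

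**Step 5: a related mismatch.** The check itself is binary (returned or not), but the review branch is headed by absence of improvement. Even with the pre-flare reference, a child who has improved without returning to baseline fits neither branch heading exactly. Only the sentence stating the check sends that child to review.

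**The case against.** The strongest case on the other side has four parts.

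- **Unseen specification.** The calculation is assigned to Appendix 9, the surveys to Appendix 8, and the workflow to the EPIC build. Any of these may lock the reference, or the baseline survey may ask about the child's usual state instead of today's symptoms. This stands as a limit on what can be claimed. It does not change what the shown rule says.
- **Context points to a pre-flare reference.** The monthly baseline questionnaire is listed among the non-exacerbation tasks that resume only on recovery. In the same list, baseline airway clearance plainly means the usual regimen. This is good evidence of intent. However, the list names only the monthly questionnaire, and the detection prompt is a separate item. If a baseline after recovery was intended, the detection prompt is worded wrongly.
- **The unchanged child.** A reader might infer that the protocol sends a child with no improvement at all straight to closure. The text does not support that. Such a child fits the review heading ("If the patient symptoms do not improve on day 10-14 (Extended Exacerbation") word for word, and a message that symptoms have improved would be untrue for that child. What stands is a conflict between two branches.
- **Safeguards.** The CF team is alerted at the trigger with the survey results. Lung function is arranged at the start and at 10-14 days. Usual care continues, and families can contact the team directly (section 5, Known potential risks). These limit the harm. Lung function is not, however, an input to the stated closure rule. The mitigation that section 5 lists for under- or over-detection, a survey based on a validated one, does not address a shifted reference.

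**Conclusion.** The point holds as a defect in a stated rule. Followed literally, section 4 allows a baseline completed during the flare to become the recovery reference. A child who is only partly better on day 10-14 would then be told that the exacerbation is over and to stop antibiotics. For an unchanged child the text is contradictory.

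This rests on two assumptions: that the family completes the prompted baseline while the child is symptomatic, and that the answers record current symptoms. A reader might go further and infer that the live system behaves this way. The documents do not show that, because Appendices 8 and 9 and the EPIC build are not available and may already apply the pre-flare reference.

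The frequency cannot be computed from the protocol. The point should be fixed because the consequence is an automated instruction to stop treatment and the correction is small. Confidence is medium, given the unseen appendices and the signs that a pre-flare reference was intended.

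**What to change.** In Protocol section 4, Description of intervention:

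1. Change the third baseline prompt so that it falls *after each exacerbation has ceased*.
2. State that the day 10-14 check uses the last baseline completed before the trigger, and that no baseline is updated while the pathway is open.
3. Reword the heading of the review branch to *have not returned to baseline*, so that the two branches match the binary check and cover every child.
4. Confirm that Appendices 8 and 9 and the EPIC build follow the same rule.

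The cost is a short wording amendment and a check of the build. If the build now uses the flare-level baseline, correcting it may bring a few more telehealth reviews for the CF team. That number cannot be estimated from the protocol.

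### The printed day 10-14 rule of the exacerbation pathway gives no clear output for a child who is better but short of baseline, and none for a child with no survey in the window

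*Protocol*

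**What the plan says.** Section 4 of the protocol (Description of intervention) sets out the pathway. It opens when a completed survey is worse than the child's latest baseline on at least two symptoms. The family then receives an automated plan naming an antibiotic and changed airway clearance and inhalation therapy, and the survey goes from twice weekly to daily. The CF team is alerted with the survey results, and home lung function by telehealth is booked: "Lung function will be performed at the start of the exacerbation and at 10-14 days later".

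At 10 to 14 days, "the program will assess if symptoms reported in the daily symptom survey have returned to baseline or not". Two branches follow.

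- The first is headed "If the patient symptoms return to (or are better than baseline) on day 10-14". The twice-weekly schedule is restored, the team is told that the exacerbation has ended, and the family gets a message "instructing them to cease antibiotics (if not already), return to baseline airway clearance and inhalation therapy".
- The second is headed "If the patient symptoms do not improve on day 10-14 (Extended Exacerbation". Its outputs are "An In Basket Message will be sent to the CF team prompting for a clinical review via telehealth" and a notice to the family "notifying them that their symptoms have not become better and expect contact from the treatment in 24 hours".

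The section adds that "The RCH EMR team have designed a workflow for the pilot to help assist in ensuring all aspects of care are completed". The content of that workflow is not printed. Appendix 9, cited for the exacerbation calculations, is not in the text at hand.

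**The concern.** The rule replaces a step that, by the protocol's own account in section 2.2, needed clinical team input in all previous studies. A program follows its conditions literally, so each foreseeable input needs a stated output.

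A missing survey is foreseeable here. Section 2.2 cites a remote monitoring study in which participant interaction fell off markedly over time. Section 5 answers the burden on families by leaving completion to their choice. Section 4 (Discontinuation of intervention) keeps non-adherent participants in the trial. The request also rises to daily while the child is unwell. Yet section 5 lists unreturned surveys as a risk only to having enough data.

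At stake is the automated prompt for clinical review in a child who was recently told to start an antibiotic and whose recovery is incomplete or unknown. A lesser matter is the survey schedule, which feeds the expected count in primary analysis 1a.

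**Working it through.** No figure in the plan needs reproducing. The check sets the assessment sentence beside the two branch conditions and asks what each child would receive.

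| Child's surveys on days 10-14 | Assessment sentence | First branch (at or better than baseline) | Second branch (do not improve) | Printed output |
|---|---|---|---|---|
| At or better than baseline | Returned | Met | Not met | Closure message, twice-weekly survey restored |
| Not improved | Not returned | Not met | Met | Review prompt, contact within 24 hours |
| Better, but short of baseline | Not returned | Not met | Not met as worded | Ambiguous: the sentence points to review, the branch heading does not |
| None returned, including a child who reported earlier and then stopped | Nothing reported to assess | Not met | Not met | None |

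The third row arises because the second branch is narrower than the negative half of the sentence that introduces it. The fourth row arises because the check runs on reported symptoms. The second branch's message, which tells the family that symptoms are no better, also presupposes a report.

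The rest of the protocol was then searched for a rule that fills the fourth row.

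- Section 4, Losses to follow-up, requires contact after a missed scheduled assessment. It is framed around the follow-up surveys and has no timing tied to the pathway.
- Lung function at 10-14 days brings contact with the respiratory laboratory. No stated rule links its result, or non-attendance, to the closure or review decision.
- Section 4, Usual Care, and section 5 leave the family able to contact the team. This depends on the family acting.

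On the schedule, only the first branch states a return to twice-weekly surveys. If a silent child is counted as still on daily surveys, each further week adds 7 expected surveys instead of 2, so 7 - 2 = 5 more are counted as missed in the percentage of analysis 1a. This is an inference: the protocol does not say how expected surveys are counted in that state.

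**The case against.** The strongest reply is that section 4 summarises a built system. Appendix 9 and the EMR workflow are where a missing-survey default would normally sit, and neither is at hand. This stands as a limit: the finding concerns the printed rule, and the system may already have a default. It does not explain why the printed branch heading is narrower than the printed assessment.

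Second, that assessment is binary, so a partly improved child has not returned to baseline and could be sent to review, with the heading taken as loose wording. That is a fair reading and is why this child is called ambiguous rather than uncovered. Stretching it to a child with no survey is harder, because nothing has been reported.

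Third, the child is not without care. The team was alerted at the trigger, lung function is repeated, usual care continues, and section 5 says that symptom data are stored in EPIC. All of this lowers the clinical weight.

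Two stronger readings are tempting, and the document supports neither.

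- A reader might infer that a silent child's antibiotics run on until the closure message arrives. The message itself allows that they may already have stopped, the prescription comes from the child's own record, and no course length is printed. Open-ended treatment cannot be inferred.
- A reader might infer that worsening on daily surveys before day 10 is ignored. The text states no action on it, but this is silence in a summary whose detailed rules are not shown, and the team may be able to see the stored surveys. A new worsening threshold would be a clinical choice for which the protocol gives no basis.

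**Conclusion.** The point holds for the printed rule. At day 10-14, partial improvement has an ambiguous output and a missing survey has none, so a child with no survey in the window gets no automated review prompt and no stated return to twice-weekly surveys. This goes beyond missing detail: the two conditions, as worded, do not match the assessment they are meant to divide, and the uncovered input is one the protocol itself expects.

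Harm is not quantified. The protocol gives no rate of exacerbations, missed daily surveys or partial recovery, and the partial cover is real. The conclusion assumes that the printed conditions are what the program applies. If Appendix 9 or the workflow sets a default, what remains is a mismatch in wording. It should be corrected, with medium confidence, as a cheap improvement.

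**What to change.** Reword the condition of the second branch in section 4 along these lines: *If symptoms are not documented as back to baseline on day 10-14, including when no survey was returned on days 10-14.* The existing In Basket prompt for clinical review then goes out for every child who does not meet the first branch.

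For non-reporters, replace the family notice, which would otherwise say that symptoms are no better, with one saying that no survey was received and to expect contact. Record their status as unknown, not as Extended Exacerbation.

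If the EMR workflow or Appendix 9 already does this, the only change is to align the wording of section 4 with it.

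The cost is one amended condition and one new family message in the EPIC build. The downside is a few extra reviews and contacts for the CF team, a workload risk that section 5 already lists. These contacts arise only in the intervention arm and add to the count compared between arms in analysis 1c, so the report should say so.
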